4.1 Visit 00 (v00)

1. Complete and review Final Eligibility Check List **[FORM 17]** and ensure that all eligibility criteria have been fulfilled before proceeding with randomization
2. Administer the Nonstudy Medications Record **[FORMS 13,14]** and confirm that participants are not taking lipid-lowering medication
3. Administer History of Vitamin and Nutritional Supplement Use Questionnaire **[FORM 15]** and confirm that participants are not taking soy, soy protein and isoflavone food supplements
4. Administer Dietary Food Frequency **[FORM 18]**
5. Administer Soy Food Questionnaire **[FORM 19]**
6. Administer 7-Day Physical Activity Recall Questionnaire **[FORM 20]**
7. Administer Center for Epidemiologic Studies Depression (CES-D) Scale **[FORM 21]**
8. Perform cognitive function assessment **[FORM 22]**
9. Obtain participants' blood pressure and pulse rate **[FORM 16]** and confirm that systolic blood pressure is ≤ 160 mmHg and diastolic blood pressure is ≤ 110 mmHg
10. Obtain and record participant's weight **[FORM 16]**
11. Measure and record waist:hip circumferences **[FORM 23]**
12. Obtain 12-lead ECG **[FORM 24]**
13. Carotid artery ultrasound examination performed (second baseline - see Section 4.2 for randomization procedure)
14. Perform urine dipstick
15. Fasting blood samples drawn and analyzed for:
 - Fibrinogen
 - vWF antigen
 - Tissue plasminogen activator (tPA)
 - Plasminogen activator inhibitor-1 (PAI-1)
 - D-dimers
 - Platelet aggregation (ADP, collagen, epinephrine)
 - Ristocetin cofactor
 - Factor VIII
 - Nattokinase
 - Anti-nattokinase antibodies
 - Erythrocyte sedimentation rate (ESR)
 - Red blood cell aggregation (plasma)
 - Red blood cell aggregability (polymer)
 - Plasma viscosity
 - Whole blood viscosity
 - Endothelial injury in-vitro assay: VCAM-1, ICAM-1
 - Monocyte activation (FACS): CD11b, CD11c, VLA-4
 - Storage
 - Plasma (EDTA) generic storage
 - Plasma (citrate) generic storage
 - Serum generic storage
 - Buffy coat
16. Active nattokinase/placebo nattokinase dispensed **[FORMS 25]**

17. Fill in the **study product ID number item** of the Eligibility Summary section on the Final Eligibility Check List **[FORM 17]** according to the randomization procedures in Section 4.2.

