7.1 Blood Specimen Collection

Participants fast prior to each clinic visit for a minimum of eight hours (nothing by mouth except for water and medications). With the participant in a seated position, blood is collected by a phlebotomist from an antecubital vein using a tourniquet in a standardized manner. After the participant has been seated for 10 minutes, the tourniquet is snugly applied to the upper arm, and the blood collected into vacutainer tubes. Once blood flow commences, the tourniquet is immediately removed to avoid prolonged occlusion of the vein. Blood is collected into 10 ml and 4 ml EDTA (1.5 mg/ml wet EDTA), 5 ml Li-heparin, 3.5 ml Na-citrate and 3.5 ml dry (with separator) vacutainer tubes depending upon the blood test required (Section 7.3). Blood tubes are inverted several times to thoroughly mix with the EDTA, Li-heparin, and Na-citrate and provided as whole blood or immediately centrifuged at 4°C or room temperature to separate the plasma. Serum that is collected in separator tubes sit at room temperature for 30 minutes prior to centrifugation. Plasma and serum are collected by low-speed centrifugation (1000 x g) for 10 minutes at 4°C or room temperature. All tubes are labeled with the participant initials, participant identification number, visit number and visit date (Section 7.2).

In addition, 3.6 ml of extra plasma (2.4 ml of EDTA plasma and 1.2 ml of citrated plasma) and 1.2 ml of extra serum is collected at baseline and at every on-trial clinic visit, prepared as described above, and stored at -80°C for future studies. The plasma and serum samples are divided into 1.2 ml aliquots and stored at -80°C in Corning cryogenic vials with screw top caps. Plasma is stored for future measurements of apolipoproteins, lipoprotein particles, Lp(a), homocysteine, nitric oxide and coagulation factors. Serum is stored for future measurements of hormones (estradiol, estrone, estrone-sulfate, testosterone, progesterone, sex hormone binding globulin and prolactin) and bone markers (bone-specific alkaline phosphatase, osteocalcin, osteoprotegrin and RANKL). The buffy coat (white blood cells) is collected at baseline and four times on-trial from EDTA plasma and stored at -80°C for future DNA studies. Urine for dipstick is collected at baseline and 1 month after randomization.

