8. The buffy coat collected at v04 is identified for apolipoprotein E genotype and stored at -80°C as outlined in the next section.
9. Plasma + EDTA, plasma + citrate and serum identified for storage at -80°C follow the protocol outlined in the next section.

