9.6.2 Baseline Comparability

All participants will be compared between treatment arms with respect to demographic (e.g., age, race, gender), cardiac and other medical history factors, cardiovascular risk factors (including blood pressure, smoking status), dietary factors, baseline CIMT, vascular stiffness, cognition, plasma insulin, lipids/CRP, hemoglobin A1c, coagulation factors, rheology parameters and inflammatory variables. Analytical methods will include two-sample t-tests (or a non-parametric analog) for continuous variables and chi-square procedures for categorical variables. The significance level for all analyses will be set at a two-sided $\alpha=0.05$.

If multiple baseline laboratory measures are completed (e.g., at SV and at v00), the baseline value will be computed as the average of the screening measure and the v00 visit determined prior to intervention. All treatment group comparisons on baseline variables will be performed for the entire randomized study sample, for the group of participants with repeat ultrasounds, and for the group of participants without repeat ultrasounds.

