9.6.5.3 Secondary Efficacy Analysis: Cognition Analyses

Three composite cognitive measures will be used to test for randomized treatment group differences in cognition; each composite will be considered as co-secondary endpoints. (1) The global composite will use scores from all neuropsychological tests. (2) The verbal memory composite will use the California Verbal Learning Test and East Boston Memory Test immediate and delayed recall scores. (3) The executive function composite (determined from principal components of prior trial data) will use scores from the Symbol Digit Modalities Test, the Trail Making Test, the Shipley Abstraction scale, Letter-Number Sequencing, and category fluency. The composites will be calculated as the average of component standardized scores weighted by the inverse interest correlation matrix. Absolute values of change from baseline on each cognitive endpoint will be calculated at both post-randomization cognitive follow-ups (18 and 36 months). General estimating equation models will be used to analyze the repeated measures of change in the cognitive endpoints. The primary independent variables will be randomized treatment group; covariates will include the CIMT randomization stratification variable as well as the baseline value of the cognitive endpoint. Differences in cognitive change will be tested by treatment group. Further analyses will test for interactions with test time (18 versus 36 months) to evaluate whether treatment effects (treatment by time interaction) vary by follow-up time.

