9.6.7.2 Modifiers of Treatment Efficacy

The extent to which treatment effects are modified by other subject-specific factors will be examined. Potential treatment effect modifiers include baseline CIMT, smoking status (on-trial smokers versus non-smokers), BMI, age and gender. The statistical significance of differences in the treatment effect by subgroup will be tested by inclusion of an interaction term (treatment by subgroup) in the efficacy models detailed above. For descriptive comparisons, treatment effect sizes will be computed for each level of the possible modifier.

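### The cognition model in 9.6.5.3 names only the CIMT stratum and the baseline score as covariates; baseline age and sex should be prespecified and the list closed, although the gain is unknown and probably modest.

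*Combined protocol and SAP*

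**What the plan says.** Section 9.6.5.3 defines three co-secondary composites (global, verbal memory, executive function) and specifies that "General estimating equation models will be used to analyze the repeated measures of change in the cognitive endpoints", at 18 and 36 months. The model has treatment group as its main term, and "covariates will include the CIMT randomization stratification variable as well as the baseline value of the cognitive endpoint". No other covariate is named, and the section does not say whether the list is complete.

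Other sections bear on this:

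- **Age and sex are available.** The baseline comparison in 9.6.2 covers factors given as "demographic (e.g., age, race, gender" and others.
- **They are used in 9.6.7.2, but in a different role.** There, "Potential treatment effect modifiers include baseline CIMT, smoking status (on-trial smokers versus non-smokers), BMI, age and gender". These enter the ancillary interaction models, not the main cognition comparison.
- **Age can affect allocation.** Section 4.2 lists age with LDL-C, smoking status and blood pressure as factors monitored within stratum. The randomization may be adapted for imbalance after 100 and after 200 participants.
- **CES-D is collected before treatment.** The steps for v00 in 4.1 include "Administer Center for Epidemiologic Studies Depression (CES-D) Scale".
- **APOE is planned.** Section 7.11.28 gives the method and 9.5.3.1 a data table. Section 7.8 says that "The buffy coat collected at v04 is identified for apolipoprotein E genotype and stored at -80°C", and 7.2 and 7.9 (item 8) say the same.
- **The buffy-coat schedule is set elsewhere.** Section 7.1 says that "The buffy coat (white blood cells) is collected at baseline and four times on-trial from EDTA plasma and stored".

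**The concern.** In a randomized comparison, baseline covariates that are fixed in advance and predict the outcome narrow the confidence interval without introducing bias. Age is the natural candidate here. Sections 1.1 and 1.2 concern cognitive decline in healthy adults, 1.1 calls dementia an age-related risk, and 1.4 sets a minimum age of 55 with no stated maximum. Age is also one of the factors that may alter allocation under 4.2, and the usual reason for adjusting for the CIMT stratum applies equally to a factor that has steered allocation.

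The second issue is that the list is not closed. If the two named covariates are all there are, age and sex are left out. If more may be added, nothing says which or when. Section 9.6.5.1 already plans for CIMT that variables judged to be confounders will be added after evaluation. The same practice applied to cognition would make the result depend on choices made with the outcome in view. At stake are some precision and the prespecification of a secondary end point measured twice after baseline in 240 randomized people.

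**Working it through.** **No stated figure to reproduce.** The documents contain no power, effect size, SD, dropout rate or R-squared for cognition, so what follows is a sensitivity calculation.

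**Inputs.** N = 240 (section 1.1). Assumed: 1:1 allocation, so 120 per arm; two-sided alpha 0.05 (stated in 9.6.2 and 9.6.3, not restated for cognition); 80% power as an anchor. The two follow-up scores are treated as a single between-group comparison. Let R² be the share of variance left after the baseline score and CIMT stratum that the added covariates explain.

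**Step 1: detectable difference under the planned model.** (1.960 + 0.842) × √(2/120) = 0.362 residual SD.

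**Step 2: gain and cost.** Adding k coefficients multiplies the variance by (1 − R²). Estimating them multiplies it by approximately 1 + k/(N − k − 5). For k = 4 the cost is 1 + 4/231 = 1.0173. For k = 2 it is 1 + 2/233 = 1.0086.

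**Step 3: net power** = Φ(2.802/√[(1 − R²) × cost] − 1.960).

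| Assumed R² | Net power, four covariates (age, sex, CES-D, APOE) | Net power, two covariates (age, sex) |
|---|---|---|
| 0.01 | 79.72% | 80.06% |
| 0.02 | 80.12% | 80.46% |
| 0.05 | 81.32% | 81.65% |
| 0.10 | 83.35% | 83.66% |

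The R² in each row is for whichever set is added. Two covariates need not reach the R² of four.

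**Step 4: break-even.** Setting (1 − R²) × cost = 1 gives R² = k/(N − 5) = k/235. That is 1.7% for four coefficients, 0.85% for two and 0.43% for one.

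**Step 5: dropout.** With an assumed 10% or 20% loss, and the anchor reset to 80% each time, net power for four covariates at R² = 0.05 is 81.25% or 81.15%. The pattern is unchanged.

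**Separate check on the APOE tube.** Section 7.9 (item 3) counts five buffy coats: baseline plus the on-trial visits at which plasma is prepared for inflammatory markers. Section 9.2.5.3 puts those visits at v02, v09, v21 and v33, and 1 + 4 = 5. Sections 7.2, 7.8 and 7.9 (item 8) take APOE from v04, which is not among the five. The schedules in 1.7 and 7.6 give APOE its own row, and in the extracted text its mark in 7.6 seems to fall at month 03. Column alignment there is unreliable, so the comparison rests on the prose sections.

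**The case against.** The planned model is standard. Adjusting change for the stratification factor and the baseline value of the same end point gives a valid, unbiased comparison, and leaving out further prognostic variables does not alter that. The baseline score probably absorbs much of what age would contribute, so the remaining R² could be below break-even. The wording on covariates is also not explicitly exhaustive. All of this stands. It limits the point to precision and prespecification, but it does not argue against naming age and sex in advance, since the worst case is a few degrees of freedom.

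A reader might go further in three ways that the documents do not support.

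- **That precision is being thrown away at no cost.** Taking R² of 3% to 10% and computing 240/(1 − R²) − 240 gives the equivalent of 7 to 27 extra participants. That R² is assumed, the range leaves out smaller values, and the cost of four coefficients is ignored. With that cost the figures are about 3 to 22, and at R² = 1% there is a small loss.
- **That omitting APOE and CES-D is an error.** The documents nowhere say that either predicts cognitive change in this population. Section 9.2.7.2 lists APOE genotype among measurements for a future date, so its availability for the efficacy analysis is not established. Including it without a missing-data rule could drop participants from the model.
- **That anyone who misses v04 has no genotype.** Genotype does not change, and 7.1 stores a baseline buffy coat for DNA work. Someone who leaves the trial before month 4 has no cognitive change score, because 9.4.3 places the first follow-up at v18. Someone who misses only v04 could be genotyped from the stored tube, although the text does not currently say so.

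**Conclusion.** The point holds as a modest improvement to the cognition analysis. Section 9.6.5.3 should name baseline age and sex and state that its list is final. The case for age rests on the documents: it is collected for everyone, 1.1 ties dementia to it, and 4.2 lets it alter allocation. Sex is not among the 4.2 factors. Its case is that it is complete, fixed before treatment and already of interest in 9.6.7.2.

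The size of the benefit is unknown. For all four candidate covariates at an assumed R² of 1% to 10%, net power changes by −0.28 to +3.35 points from an assumed 80%. The added cost is about 0.4% of residual variance per coefficient. These figures depend on the assumed R², allocation ratio, alpha and power anchor.

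The v04 discrepancy is real, but it is a sample-handling matter and lends no support to the precision argument.

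**What to change.** In 9.6.5.3, state that the covariates for all three composites are the CIMT stratum, the baseline value of the composite, baseline age and sex, and that no others will be added to the main analysis. Specify how age enters (for example, linear in years). If CES-D or APOE e4 carriage is wanted, name it now with a rule for missing values; otherwise leave it for sensitivity analyses. This costs a few lines in the SAP, settled before unblinding, and needs no new data.

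As a minor correction, reconcile 7.2, 7.8 and 7.9 (item 8) with 7.1, 7.9 (item 3) and 9.2.5.3 on which buffy coat supplies APOE, and check the APOE rows in the 1.7 and 7.6 schedules. Genotyping the stored v00 buffy coat would resolve the conflict without another draw. If v04 is intended, list it as an added collection and name the baseline tube as backup.

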9.6.5.4 Analysis of Clinical Events, Adverse Experiences, and Safety Measures

The following clinical events will be tabulated and compared between treatment groups using chi-square or Fisher's exact methods:

- 1) Major cardiovascular events: fatal/nonfatal MI, sudden coronary death, hospitalization for unstable angina, and revascularization procedures (CABG and PTCA).
- 2) Major cerebrovascular events: TIA, RIND, CVA.
- 3) Deep vein thrombosis.
- 4) Pulmonary thromboembolism.
- 5) Incident cancers.
- 6) All cause mortality and cause-specific mortality, including cardiovascular, cerebrovascular, peripheral vascular, cancer, other medical, and non-medical and non-coronary mortality.
- 7) The treatment groups will also be compared for standard clinical and laboratory safety tests.

In the analysis of laboratory safety variables, treatment groups will be compared with regard to proportions of participants with clinically meaningful changes (either increase or decreases from normal range). Analyses of these data will be done using a chi-square test or Mantel-Haenszel test that allows for stratification, as appropriate.

9.6.6 Interim Analysis

At each meeting of the EDSMB, summary tables of safety data (Section 9.5.2.4) without any formal statistical analyses will be reviewed. The EDSMB will be masked to treatment assignment (i.e., the treatments will be labeled as A and B). If in the best judgment of the EDSMB, trends or patterns are observed in the safety data, the EDSMB may request a formal statistical analysis of the data. The Lan-DeMets rule to determine the current (and all future) alpha levels will be used. Early termination is predicated on attaining statistical significance on major safety issues to be defined by the EDSMB.

Interim analyses will not be performed on the primary (CIMT, arterial stiffness) and secondary (cognition) trial outcomes.

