1.3 Study Overview

The Nattokinase Atherothrombotic Prevention Study (NAPS) is a randomized, double-blinded, placebo-controlled, non-invasive vascular imaging trial. A total of 240 healthy non-demented women and men without clinical evidence of CVD or diabetes mellitus will be randomized to either placebo or to active oral nattokinase 2,000 fibrinolytic units daily. Recruitment will occur over 2 years and the treatment period will be for 3 years. Candidates will be prescreened, seen for 1 screening visit to determine eligibility and then randomized at a baseline visit. Participants will then return for a follow-up visit 1 week after randomization and then will be followed monthly for the first 6 months and then every 3 months for the remainder of the trial. Rate of change in distal common carotid artery (CCA) far wall intima-media thickness (CIMT) and arterial stiffness in computer image processed B-mode ultrasonograms will be the co-primary trial end points. Cognitive decline determined with a neuropsychological battery designed to evaluate 7 cognitive domains including: attention, concentration, working memory, executive function; visuospatial/visuoconstructive skills; naming/semantic memory; and verbal and nonverbal episodic memory will be the secondary trial endpoint. Other endpoints will include blood pressure, hemostatic, fibrinolytic and hemorheological factors as well as platelet activity and biomarkers for inflammation, monocyte activation, vascular endothelium injury and activation of vascular endothelium by circulating monocytes.

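### Section 9.6.6 makes early termination for safety conditional on statistical significance, which for rare serious events in 240 people needs a lopsided split; the test should be advisory

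*Combined protocol and SAP*

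**What the plan says.** Section 9.6.6 (Interim Analysis) sets out a sequence.

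- At each meeting the EDSMB reviews summary safety tables without formal testing. The board is masked: "The EDSMB will be masked to treatment assignment (i.e., the treatments will be labeled as A and B").
- Judgment enters at the next step. If "trends or patterns are observed in the safety data, the EDSMB may request a formal statistical analysis of the data".
- The alpha for that analysis then follows a spending approach: "The Lan-DeMets rule to determine the current (and all future) alpha levels will be used".
- The stopping condition comes last: "Early termination is predicated on attaining statistical significance on major safety issues to be defined by the EDSMB".

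The same section rules out interim analysis of CIMT, arterial stiffness and cognition.

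The section names no spending function, total alpha, sidedness, look schedule or event definition. Section 9.6.5.4 allows chi-square or Fisher's exact test for clinical events. Sections 6.12.2 and 9.5.2.4 cover only the reporting of safety data to the board. Sections 6.2, 6.4 and 6.9 deal with whether an individual participant continues, not with stopping the trial.

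**The concern.** The wording states a condition. The board's judgment decides whether a test is requested, but the test result decides whether the trial may stop. A board that follows the text would have to wait for significance even when an imbalance in deaths or strokes was clinically convincing.

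This matters here because the participants are healthy, the agent is studied for antithrombotic and fibrinolytic effects (section 1.1), and treatment lasts three years. With 240 people, a test on a rare event has little power, so failing to reach significance says little about whether harm is present. The usual reason to guard alpha at interim, protecting the efficacy conclusion, does not apply because no efficacy outcome is examined.

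**Working it through.** **Inputs from the documents.** Section 1.3 gives the sample size ("A total of 240 healthy non-demented women and men without clinical evidence of CVD or diabetes mellitus will be randomized") and two arms ("randomized to either placebo or to active oral nattokinase 2,000 fibrinolytic units daily"). Section 9.6.5.4 gives the test, chi-square or Fisher's exact. The plan has no safety boundary or power figure to reproduce.

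**Assumptions.**
- Allocation is 1:1, so 120 per arm; the ratio is not stated.
- Total safety alpha is two-sided 0.05. That level is stated in sections 9.6.2 ("The significance level for all analyses will be set at a two-sided" 0.05) and 9.6.3, for baseline and on-trial comparisons, and not for safety stopping.
- A first look at half information (t = 0.5) serves as the example.

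**Step 1: alpha available at t = 0.5.**
- Pocock type: 0.05 × ln(1 + (e − 1) × 0.5) = 0.0310.
- O'Brien-Fleming type, spending 0.05 through one function: 2[1 − Φ(1.96/√0.5)] = 0.0056.
- O'Brien-Fleming type, spending 0.025 on each side: 2 × 2[1 − Φ(2.241/√0.5)] = 0.0031.

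The two O'Brien-Fleming figures are different common conventions; the plan does not choose between them.

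**Step 2: smallest split that passes, two-sided Fisher, 120 per arm.**

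| Alpha | No events in the other arm | One event in the other arm |
|---|---|---|
| 0.05, no penalty for looks | 6 v 0 (p = 0.029); 5 v 0 fails (0.060) | 8 v 1 (0.036); 7 v 1 fails (0.066) |
| 0.0310 (Pocock) | 6 v 0 (0.029) | 9 v 1 (0.019) |
| 0.0056 (O'Brien-Fleming) | 9 v 0 (0.0033) | 11 v 1 (0.0052) |
| 0.0031 (O'Brien-Fleming) | 10 v 0 (0.0016); 9 v 0 fails (0.0033) | 12 v 1 (0.0027) |

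With only 60 per arm, 9 v 0 gives p = 0.0028 and passes under either O'Brien-Fleming convention.

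**Step 3: more lenient choices.** Uncorrected chi-square at 0.05 passes 4 v 0 (p = 0.044) and 7 v 1 (p = 0.031). With 4 events in total, the expected count is 2 per arm, so the approximation is poor. One-sided Fisher at 0.05 passes 5 v 0 (p = 0.030) and 7 v 1 (p = 0.033).

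**Step 4: power.** The documents give no event rates, so these are assumed. Exact enumeration, Fisher, 120 per arm:

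| True rates | 0.05 | 0.0310 | 0.0056 |
|---|---|---|---|
| 1% v 3% | 5.7% | 5.0% | 0.3% |
| 1% v 5% | 28% | 23% | 6% |
| 2% v 6% | 22% | 17% | 5% |
| 5% v 10% | 22% | 18% | 6% |
| 1% v 10% | 86% | 81% | 59% |

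A tripling from 2% to 6% is found about one time in five at the full 0.05. By the normal approximation, 80% power for it would need about 376 per arm.

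**Step 5: common events.** At 0.05, 24 v 12 passes (20% v 10%, p = 0.046). At 0.0056, 30 v 12 is needed (p = 0.0035).

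**The case against.** Four objections carry weight.

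1. **The rule has a purpose.** A reader might infer that, with no efficacy look, it does nothing except tie the board's hands. The documents do not support that. Section 9.5.2.4 lists 13 safety categories reported cumulatively, and the board sees them at each meeting. Alpha spending limits the chance of stopping on noise across those looks. This stands. It supports a boundary as guidance, but does not require making it a precondition.

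2. **The threshold depends on choices the plan does not make.** It is tempting to take 10 v 0 as the trial's bar. That figure needs O'Brien-Fleming-type spending, one particular convention, Fisher's test and a look at half information. Under Pocock-type spending the bar with no events in the other arm stays at 6 v 0, as at unadjusted 0.05. This stands, and the result has to be given as a range.

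3. **The board defines the safety issues.** A reader might infer that any safety stop needs a very lopsided run. That holds only for rare events tested singly. The board could choose a composite or a commoner outcome, such as questionnaire bleeding or out-of-range clotting tests, where roughly 2:1 may suffice. This stands as a limit on scope. It does not help with deaths or strokes if these are few.

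4. **The text restricts termination only.** It does not bar other recommendations, such as closer monitoring or a pause, so saying the board could not act at all would go too far. Further terms for the board may also sit in the organizational structure section or a charter, neither of which was available for review. A charter that allowed stopping without significance would, however, conflict with section 9.6.6 as worded.

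**Conclusion.** The point holds for rare serious events. Section 9.6.6 makes significance a precondition for stopping, and no other safety route to termination appears in the text available for review. The required split is about 6 v 0 or 8 v 1 on Fisher's test at two-sided 0.05, about 6 v 0 under Pocock-type spending at half information, and 9-10 v 0 or 11-12 v 1 under O'Brien-Fleming-type spending at half information. Uncorrected chi-square would lower the unadjusted bar to 4 v 0 or 7 v 1, but should not be relied on at those counts.

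The size rests on 1:1 allocation, a total two-sided alpha of 0.05, and a spending function and test that the plan leaves open; the power figures also rest on assumed event rates. The exact threshold moves with these choices. The conditional wording applies under all of them. This is a cheap improvement to the wording and does not affect the efficacy analysis.

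**What to change.** In section 9.6.6, replace the sentence that ties early termination to significance with wording such as: the EDSMB may recommend termination on the totality of the safety data; any Lan-DeMets-adjusted test is supporting guidance and not a precondition. Any EDSMB charter should say the same.

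If the Lan-DeMets boundary is kept as guidance, name the spending function, total alpha, sidedness, test, look schedule and the events to be tested, so that the board knows its reference values in advance. Bleeding deserves explicit mention: it is reported to the board under section 9.5.2.4 but is not named in the list of between-group event comparisons in section 9.6.5.4.

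The core change is one sentence, with no effect on sample size, data collection or the efficacy analysis. The downside is a slightly higher chance of stopping on a chance imbalance, which the board's judgment and the advisory boundary would temper.
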